## DOCUMENT HISTORY OF REVISIONS

Type of amendment	Protocol version number	Final version date	Nature of amendments
Not applicable	1.0	20 December 2016	Not applicable
Amendment 1	2.0	10 January 2022	
1) Update of the study team and its affiliations with the addition of [name] and [name] as study secretariat, as well as [name] and [name] among study statisticians.
 
2) Among primary objectives, revision of the definition of “incidence of pregnancy” and the way to analyze it; current definition is “rate of pregnancy” to be analyzed according to the Kaplan-Meier method.
 
3) Addition of the three following secondary objectives (and respective statistical analyses):
 
 
- To describe baseline, tumor and treatment characteristics as well as patterns of care including access to risk-reducing surgeries in BRCA mutated patients.
 
- To evaluate the prognostic impact of baseline, tumor and treatment characteristics as well as of risk-reducing surgeries in BRCA mutated patients.
 
- To evaluate tumor infiltrating lymphocytes (TILs) in BRCA mutated patients.
 
 
4) Clarification and update of study eligibility criteria: accrual is allowed for patients diagnosed up to December 2020, while patients with invasive breast cancer and germline BRCA variants of unknown significance are excluded.
 
5) Inclusion of the following information for data collection: cause of death.

			
6) Clarification of the priority for the analysis of survival endpoints: DFS is the primary endpoint and BCSS/OS are secondary endpoints.
 
7) Clarifications of the type of survival analyses to be conducted for reducing the impact of selection bias (i.e. guaranteed time bias). Two analyses are expected: the extended Cox model analysis with occurrence of pregnancy as a time-varying covariate and a “case-control” analysis. Type of matching for the “case-control” analysis has been clarified and will be performed according to the following factors: disease-free interval, year at diagnosis, nodal status, hormone receptor status and type of BRCA mutation are the matching criteria.
 
8) Addition of the ClinicalTrials.gov identifier of this study: NCT02308085.
 
9) Corrections of typos and inconsistencies within the text.
 
10) Addition of 2 columns in the excel file for data collection
 
11) Updated list of participating centers.

--	--	--	--

## SYNOPSIS

Title of the study	A multicenter retrospective study on the prognostic impact of pregnancy in women with history of BRCA mutated breast cancer
Protocol version	2.0 – 10 January 2022
Sponsor	Institut Jules Bordet, Brussels, Belgium
Study chairs	
 
• [name] PhD, IRCCS Ospedale Policlinico San Martino – University of Genova
 
• [name] PhD, Institut Jules Bordet
 
• [name], MD PhD, Hospital Zambrano Hellion Tecnológico de Monterrey
 

Study Objectives	
Primary objectives:
 
 
- To evaluate the prognostic impact of pregnancy following breast cancer diagnosis in BRCA mutated patients.
 
- To evaluate the rate of pregnancy following breast cancer diagnosis in BRCA mutated patients.
 
 
Secondary objectives:
 
 
- To evaluate the prognostic impact of pregnancy following breast cancer diagnosis in various subgroups of BRCA mutated patients according to:                             
 
• Type of BRCA mutation;
 
• Hormone receptor status;
 
• HER2 status;
 
• Exposure to chemotherapy;
 
• Exposure to endocrine therapy;
 
• Interval between diagnosis and pregnancy;
 
• Outcome of pregnancy;
 
• Breastfeeding status.
 
 
 
- To evaluate the pregnancy, fetal and obstetrical outcomes of the pregnancies following breast cancer diagnosis in BRCA mutated patients.
 

	
 
- To evaluate the safety of assisted reproductive technology (ART) procedures following breast cancer diagnosis in BRCA mutated patients.
 
- To evaluate the impact of anticancer therapies on patients' ovarian function.
 
- To describe baseline, tumor and treatment characteristics as well as patterns of care including access to risk-reducing surgeries in BRCA mutated patients.
 
- To evaluate the prognostic impact of baseline, tumor and treatment characteristics as well as of risk-reducing surgeries in BRCA mutated patients.
 
- To evaluate tumor infiltrating lymphocytes (TILs) in BRCA mutated patients.
 

Number of patients	More than 2000 non-pregnant BRCA mutated breast cancer patients and more than 200 pregnant BRCA mutated breast cancer patients (estimated numbers, considering a rate of pregnancy of approximately 10%).
Eligibility criteria	
Inclusion criteria:
 
 
- Diagnosis of invasive breast cancer between January 2000 and December 2020;
 
- Breast cancer diagnosis at the age of <math>\leq 40</math> years;
 
- Known presence of germline BRCA pathogenic variant.
 
 
Exclusion criteria:
 
 
- Known BRCA mutation with no diagnosis of invasive breast cancer;
 
- Diagnosis of ovarian cancer or other malignancies with no history of invasive breast cancer;
 
- Diagnosis of hereditary or familial invasive breast cancer without BRCA mutation or with BRCA genes not tested;
 
- Diagnosis of invasive breast cancer with germline BRCA variants of unknown significance.
 

Design of the trial	Retrospective multicenter hospital-based study


Statistics
	
The achievement of pregnancy after diagnosis of breast cancer will be the criteria used to distinguish between two cohorts of patients: women with no subsequent pregnancies after breast cancer diagnosis (“non-pregnant cohort”), and women with one or more pregnancies any time after breast cancer diagnosis (“pregnant cohort”). To evaluate the prognostic impact of pregnancy following breast cancer diagnosis in BRCA mutated survivors, three survival endpoints will be considered in the two cohorts: disease-free survival (DFS, as primary endpoint) breast cancer specific survival (BCSS, as secondary endpoint) and overall survival (OS, as secondary endpoint). To reduce the impact of selection bias (i.e. guaranteed time bias), two analyses will be performed. In the extended Cox model analysis with occurrence of pregnancy as a time-varying covariate, all eligible patients included in the study will be considered. In the “case-control” analysis, each patient in the pregnant cohort (case) will be matched with 3 patients from the non-pregnant cohort (controls). Each nonpregnant control should have a disease-free interval equal to or longer than the time elapsing between breast cancer diagnosis and date of pregnancy of the matched pregnant case. Patients who became pregnant after the date of the DFS event will be dropped from this analysis. The other matching factors will be year at diagnosis (<math>\pm 2.5</math> years), nodal status (negative vs. positive), hormone receptor status (positive vs. negative), and type of BRCA mutation (BRCA1 vs. BRCA2). Because all included patients are aged <math>\leq 40</math> years at the time of diagnosis, matching according to age will not be performed. The matching will be done centrally at the coordinating center. The prognostic impact (in terms of DFS, BCSS and OS) of pregnancy following breast cancer diagnosis will be then evaluated in various subgroups of BRCA mutated survivors. Pregnancy rate will be computed according to the Kaplan-Meier method.

--------------------------	---

## 1. BACKGROUND AND SCIENTIFIC RATIONALE

Breast cancer is the most common tumor type diagnosed in women of reproductive age [1]. The inheritance of a mutation in one of the breast cancer susceptibility genes (i.e. *BRCA1* or *BRCA2*) generates the hereditary breast and ovarian cancer syndrome [2]. For healthy women with *BRCA1* mutated gene (i.e. *BRCA1* carriers), the average lifetime risk of developing breast and ovarian cancer is approximately 67% and 45%, respectively; for *BRCA2* carriers, these average cumulative risks are 66% and 12%, respectively [3].

Since young women with breast cancer, including those with *BRCA* mutation, are more likely to develop biologically aggressive tumors [4], the majority of them are candidates to receive antineoplastic treatments that include chemotherapy. The use of cytotoxic therapy in premenopausal patients may result in the occurrence of treatment-related premature ovarian failure (POF) [5]. *BRCA* mutations seem to negatively affect ovarian reserve with consequent accelerated ovarian aging [6]. Although very limited data are available on this topic, it has been suggested that *BRCA* carriers may be more sensitive to the gonadotoxic effect of chemotherapy as compared to patients without mutations with subsequent higher risk of developing this side effect [6]. The impairment in ovarian function negatively impacts on global health of young breast cancer survivors being associated with several side effects including infertility [7].

Concerns about fertility preservation and future chance of achieving a pregnancy are prevalent issues affecting young breast cancer patients [8]. Hence, accordingly, major international guidelines recommend physicians to address with patients as part of informed consent before anticancer therapies the possibility of developing POF and infertility, and then to discuss fertility preservation options in interested patients [9–11]. Specific issues on this regard should be considered in patients with *BRCA* mutation in the context of their unique concerns [12]. For carriers, given the increasing risk of ovarian cancer with age, bilateral salpingo-oophorectomy is generally recommended for both *BRCA1* and *BRCA2* carriers between the ages of 35 and 40 years and upon completion of childbearing [13]. Moreover, some carriers wish to eliminate the mutation from future offspring through pre-implantation genetic diagnosis [14]. Finally, given the increasing risk of ovarian and breast cancer and the risk of developing long-term treatment-related POF [15], the window for fertility and pregnancy may be narrow in such young women. Of note, although, the last years have brought many safety and efficacy data on the available options for fertility preservation increasing the chances of

future offspring in cancer survivors, numerous challenges remain for young breast cancer patients considering fertility preservation and to have a pregnancy after the end of treatments, especially for those with *BRCA* mutations. Thus, further research is needed in the field; particularly, reproduction studies to address the specific issues of women with *BRCA* mutations are lacking and should be considered a research priority.

Approximately 40% to 50% of women in whom breast cancer is diagnosed during childbearing age wish to have a subsequent pregnancy [16]. However, the percentage of breast cancer patients reported in the literature that has at least one full-term pregnancy after breast cancer diagnosis is very low. Of note, among cancer survivors, breast cancer patients have the lowest pregnancy rate with an overall 67% reduction in the chance of giving birth after cancer treatment as compared to the general population [17]. This observation reflects not only the damage to ovarian reserve due to the gonadotoxic treatments required, but also patient and provider concerns related to a possible negative impact of pregnancy on the evolution of breast cancer [18].

Recent data support the statement that pregnancy in cancer survivors after adequate treatment and follow-up should not be discouraged including among patients with breast cancer [19]. As shown in a meta-analysis of 14 retrospective control-matched studies, breast cancer patients who became pregnant following diagnosis and treatment had a 41% reduced risk of death compared to women who did not get pregnant (pooled relative risk [PRR], 0.59; 95% confidence intervals [CI], 0.50-0.70) [20]. Furthermore, a more recent multicenter retrospective cohort study confirmed the safety of pregnancy after breast cancer even in patients with endocrine-sensitive disease [21]. Importantly, no impact of abortion on patient outcome was observed either [21]. Nevertheless, in the specific subgroup of patients with *BRCA* mutations very limited data consisting in one single study are available on the impact of pregnancy on breast cancer survival [22]. In this study, out of the 128 pregnant cases included, only 53 had a pregnancy following breast cancer; no difference in breast cancer specific mortality was observed between pregnant cases and matched non-pregnant control (adjusted hazard ratio [HR], 0.73; 95% CI, 0.21-2.68) [22]. However, due to the limited number of patients included in the analysis, no solid conclusion can be drawn from this study to counsel *BRCA* mutated survivors on the safety of having a pregnancy after breast cancer diagnosis. Furthermore, no information is available on the impact of breastfeeding in these patients, and it remains not clear yet the ideal interval to wait between the end of anticancer treatments and conception. Moreover, other

highly relevant issues remain elusive pertaining on subsequent pregnancy in *BRCA* mutated breast cancer patients, including the safety of assisted reproductive technology (ART), pregnancy outcomes, risk of congenital malformations, breastfeeding patterns and many more.

Thus, due to the lack of data on several issues on this regard, the present study aims at refining the understanding of the effect of pregnancy on breast cancer outcomes in the specific population of *BRCA* mutated patients with known history of breast cancer.

## 2. STUDY OBJECTIVES

### Primary objectives:

- To evaluate the prognostic impact of pregnancy following breast cancer diagnosis in *BRCA* mutated patients. The following survival endpoints will be considered: disease-free survival (DFS, as primary endpoint), breast cancer specific survival (BCSS, as secondary endpoint) and overall survival (OS, as secondary endpoint).
- To evaluate the rate of pregnancy following breast cancer diagnosis in *BRCA* mutated patients.

### Secondary objectives:

- To evaluate the prognostic impact (in terms of DFS, BCSS and OS) of pregnancy following breast cancer diagnosis in various subgroups of *BRCA* mutated patients according to:
  - Type of *BRCA* mutation: *BRCA1* vs. *BRCA2*;
  - Hormone receptor status: positive vs. negative;
  - HER2 status: positive vs. negative;
  - Exposure to chemotherapy: prior exposure vs. no prior exposure;
  - Exposure to endocrine therapy: prior exposure vs. no prior exposure;
  - Interval between diagnosis and pregnancy:  $\leq 2$  years vs.  $> 2$  years after diagnosis;
  - Outcome of pregnancy: abortion vs. completed pregnancy;
  - Breastfeeding status: breastfeeding vs. no breastfeeding.
- To evaluate the pregnancy, fetal and obstetrical outcomes of the pregnancies following breast cancer diagnosis in *BRCA* mutated patients.
- To evaluate the safety of ART procedures following breast cancer diagnosis in *BRCA* mutated patients.

- To evaluate the impact of anticancer therapies on patients' ovarian function, in terms of incidence of treatment-induced POF and age at menopause.
- To describe baseline, tumor and treatment characteristics as well as patterns of care including access to risk-reducing surgeries in *BRCA* mutated patients.
- To evaluate the prognostic impact of baseline, tumor and treatment characteristics as well as of risk-reducing surgeries in *BRCA* mutated patients.
- To evaluate tumor infiltrating lymphocytes (TILs) in *BRCA* mutated patients.

### 3. METHODOLOGY

This is a multicenter hospital-based retrospective cohort study (ClinicalTrials.gov identifier: NCT02308085) conducted across several Institutions managing patients with hereditary breast cancer. The study aims to refine the understanding of the effect of pregnancy on breast cancer outcomes in *BRCA* mutated patients with known history of breast cancer.

#### 3.1. Eligibility criteria

The eligibility criteria are intentionally broad for trying to exclude as few patients as possible so that true population-based data can be obtained. To be eligible for the present study, patients should fulfill the following inclusion and exclusion criteria.

##### Inclusion criteria:

- Diagnosis of invasive breast cancer between January 2000 and December 2020;
- Breast cancer diagnosis at the age of  $\leq 40$  years;
- Known presence of germline *BRCA* pathogenic variant.

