##### Exclusion criteria:

- Known *BRCA* mutation with no diagnosis of invasive breast cancer;
- Diagnosis of ovarian cancer or other malignancies with no history of invasive breast cancer;
- Diagnosis of hereditary or familial invasive breast cancer without *BRCA* mutation or with *BRCA* genes not tested;
- Diagnosis of invasive breast cancer with germline *BRCA* variants of unknown significance.

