### 3.3. Data collection

For all consecutive eligible patients included in the study from each participating Institution, their medical records will be retrieved and anonymized data entered into a database. The following information will be collected, if available:

- 1) Baseline characteristics: body mass index; smoking habit; age at menarche; age at menopause; menopausal status at the time of breast cancer diagnosis; use of birth control pills; prior children before breast cancer diagnosis; history of spontaneous abortion; history of induced abortion; prior treatment for infertility; prior gynecological surgery and/or medical history with possible impact on fertility.
- 2) Breast cancer history: date of diagnosis; age at diagnosis; disease stage; laterality of the primary tumor; type of breast and axillary surgery; use of breast reconstruction surgery; grade; histology; tumor size and nodal status (for patients who underwent primary systemic therapy, only clinical tumor size and nodal status will be collected); hormone receptor status (estrogen and progesterone receptors); HER2 status.
- 3) Treatment of the primary tumor: timing of systemic therapy administration; use of chemotherapy (type and number of cycles); use of endocrine therapy (type and duration); use of anti-HER2 targeted therapy (type and duration); use of radiotherapy.
- 4) Survival status: any recurrence of invasive breast cancer including date of the event; any second primary breast cancer including date of the event; any second primary malignancy including date of the event; date of last follow-up and/or death; cause of death (breast cancer-related or not).
- 5) Ovarian function after chemotherapy: treatment-induced POF; age at menopause.

6) Pregnancy after breast cancer: any pregnancy including date of the event; pregnancy outcome; gestational age at delivery; any pregnancy/fetal/birth complications; breastfeeding and its duration; use and type of ART.

7) BRCA mutation: date of *BRCA* testing; type of *BRCA* mutation; use and date of breast prophylactic surgery; use and date of gynecological prophylactic surgery.

8) Additional information: diagnosis of breast cancer during pregnancy, availability of digital scanned images for TILs analysis

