## 4. STATISTICS

The achievement of pregnancy after diagnosis of breast cancer will be the criteria used to distinguish between two cohorts of patients: women with no subsequent pregnancies after breast cancer diagnosis (“non-pregnant cohort”), and women with one or more pregnancies any time after breast cancer diagnosis (“pregnant cohort”). Pregnancies could have resulted in live births, therapeutic or spontaneous abortions.

More than 2000 non-pregnant *BRCA* mutated breast cancer patients and more than 200 pregnant *BRCA* mutated breast cancer patients are expected to be included in the present study (estimated numbers, considering an incidence of pregnancy of approximately 10%).

To evaluate the prognostic impact of pregnancy following breast cancer diagnosis in *BRCA* mutated survivors, three survival endpoints will be considered in the two cohorts: DFS (as primary endpoint) BCSS (as secondary endpoint) and OS (as secondary endpoint). DFS event is defined by the occurrence of one of the following invasive events: local recurrence, distant metastases, contralateral or ipsilateral breast tumor, second primary malignancy, or death from any cause. BCSS event is defined as death from breast cancer. OS event is defined as death from any cause. For DFS, observation times of patients without the event will be censored on the date of their last contact. Using individual patient data from all patients included in the study, survival outcomes of patients in the

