pregnant cohort will be compared to those of patients in the non-pregnant cohort. To reduce the impact of selection bias (i.e. guaranteed time bias), two analyses will be performed. In the extended Cox model analysis with occurrence of pregnancy as a time-varying covariate, all eligible patients included in the study will be considered. In the “case-control” analysis, each patient in the pregnant cohort (case) will be matched with 3 patients from the non-pregnant cohort (controls). To adjust for guaranteed time bias, each patient in the non-pregnant cohort should have a disease-free interval equal to or longer than the time elapsing between breast cancer diagnosis and date of pregnancy of the matched patient in the pregnant cohort. Patients who became pregnant after the date of the DFS event will be dropped from this analysis. Patients will be also matched according to several variables including type of *BRCA* mutation (*BRCA1* vs. *BRCA2*), hormone receptor status (positive vs. negative), nodal status (negative vs. positive), and year at diagnosis ( $\pm 2.5$  years). Because all included patients are aged  $\leq 40$  years at the time of diagnosis, matching according to age will not be performed. The matching will be done centrally at the coordinating center. Two data sets will be constituted: one for the cases and one for the potential controls. Cases will be sorted randomly and matching will be done starting for the first case until the last one. For each case, all possible controls will be extracted from the data set of potential controls. If they are only 2 controls available, matching criteria will be relaxed one by one (starting from year of diagnosis, etc) until at least a third control is found. It is anticipated, given the expected low rate of cases in the full database, to reach matching for almost each case. In these analyses, all survival endpoints will be calculated from the date of pregnancy until the date of the event. In the non-pregnant cohort, survival endpoints will be calculated from the date of diagnosis, adding the time elapsing between diagnosis and pregnancy of the matched pregnant case.

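### Women with metastatic disease at diagnosis enter the survival comparisons of pregnancy, and the plan has no rule for scoring their DFS

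*Combined protocol and SAP*

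**What the plan says.** Section 3.1 admits any woman with "Diagnosis of invasive breast cancer between January 2000 and December 2020", diagnosed at 40 or younger, with a known germline BRCA pathogenic variant. The four exclusions concern absence of invasive breast cancer, absent or untested BRCA mutation, and variants of unknown significance. Neither list mentions stage, and the Synopsis repeats both unchanged. The breadth is deliberate: "The eligibility criteria are intentionally broad for trying to exclude as few patients as possible".

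Section 3.3 collects stage ("disease stage; laterality of the primary tumor"), but no section uses it to define an analysis set. Stage is not a matching factor in Section 4, and the multivariable Cox models there name no covariates.

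In Section 4 the extended Cox model, with pregnancy as a time-varying covariate, has this population: "all eligible patients included in the study will be considered". On the endpoint, "DFS event is defined by the occurrence of one of the following invasive events", and the list is "local recurrence, distant metastases, contralateral or ipsilateral breast tumor, second primary malignancy, or death from any cause". On censoring: "For DFS, observation times of patients without the event will be censored on the date of their last contact". Nothing covers a woman whose metastases are present on the day of diagnosis.

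In the matched analysis, a control needs a disease-free interval at least as long as her case's time from diagnosis to pregnancy, and women who conceived after a DFS event are dropped.

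**The concern.** A woman with stage IV disease at diagnosis is eligible and is analysed, but her DFS can be scored in at least three ways: as an event on day 0, as an event at later progression or death, or by leaving her out. The survival-status items in Section 3.3 cover recurrence, second primaries, last follow-up and death. They have no field for progression of disease that was never cleared, so a woman with no recorded recurrence could count as disease-free until death or last contact. Sites may resolve this differently, and the primary endpoint depends on the choice.

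The second issue is direction. If these women seldom conceive, they contribute high-risk person-time to the unexposed state and almost none to the exposed state. That makes pregnancy look safer than it is, which is the unfavourable direction of error for a study meant to inform counselling on safety.

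**Working it through.** **1. The plan's own figure.** Inputs from Section 4: 2000 non-pregnant and 200 pregnant women, 65% DFS at 5 years in the non-pregnant cohort, two-sided 0.05, stated power 0.83 (HR 0.75) and 0.62 (HR 0.80).

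- Exponential hazard: −ln(0.65)/5 = 0.0862 per year.
- With 10 years of follow-up for every woman, the non-pregnant event probability is 1 − 0.65² = 0.5775, giving 2000 × 0.5775 = 1155 events.
- Pregnant cohort at HR 0.75: 200 × (1 − 0.4225^0.75) = 95.2 events, so D ≈ 1250. At HR 0.80: 99.6 events, so D ≈ 1255.
- Schoenfeld: power = Φ(√(D·p·(1−p))·|ln HR| − 1.96), with p = 200/2200 = 0.0909.
- HR 0.75: √(1250 × 0.0826) = 10.16; 10.16 × 0.2877 − 1.96 = 0.964; power 0.8325.
- HR 0.80: 10.18 × 0.2231 − 1.96 = 0.312; power 0.6226.

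Both stated figures are reproduced. (Uniform 20-year accrual with 30 years in total would give 1738 events and 0.932 / 0.764. That is a separate matter.)

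**2. Bias in the extended Cox model.** The documents give no stage IV share, prognosis or conception rate, so these are assumptions: 2%, 5% or 8% stage IV; no conception among them; median time to a later event of 1, 3 or 5 years; 5-year OS of 85% or 90% in non-metastatic women; DFS in non-metastatic women as in step 1. Each simulated study has 2200 women, about 10–15% of whom conceive. Follow-up is either 10 years for all or spread over 2–22 years. Time runs from diagnosis, the true pregnancy HR is 1.0, and there are 400–500 runs per scenario. Ranges run over the follow-up, median and OS settings.

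| Stage IV share | DFS HR, later event | DFS type I error | OS HR | OS type I error |
|---|---|---|---|---|
| 0% | 0.998 | 3.2–3.4% | 0.99–1.00 | 5.0–6.0% |
| 2% | 0.98–0.99 | 2.6–6.4% | 0.92–0.99 | 2.6–7.8% |
| 5% | 0.96–0.98 | 3.8–5.6% | 0.85–0.97 | 4.2–13.0% |
| 8% | 0.93–0.97 | 4.6–10.0% | 0.79–0.95 | 4.4–22.4% |

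Monte Carlo standard errors are about 0.005 for the DFS HR, 0.005–0.009 for the OS HR, and about 1 percentage point for a type I error near 5%.

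Scored instead as a DFS event on day 0, stage IV women leave the HR at 0.998–1.004. Nobody is pregnant in those risk sets, so the events carry no information on the HR.

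OS is hit harder because deaths are scarcer. At 8% stage IV, median 3 years, 10-year follow-up and 90% OS, stage IV women supply 159 of 543 deaths (29%). In the matching DFS scenario they supply 159 of 1328 events (12%). BCSS was not simulated; as an endpoint of deaths it should behave more like OS than DFS.

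**3. The 5-year DFS rate.** If 65% describes non-metastatic women, day-0 scoring gives a mixed rate of 0.65 × (1 − f): 63.7%, 61.8% and 59.8% at f = 2%, 5% and 8%.

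**4. The matched analysis.** With the disease-free interval set to zero, a stage IV woman can never be a control. If the interval is built from the recorded recurrence and death dates, she can. The plan does not say which applies.

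**5. Power after restriction.** Removing 2%, 5% or 8% of the non-pregnant women leaves 1960, 1900 or 1840. For 8%: D = 1840 × 0.5775 + 95.2 = 1158; p = 200/2040 = 0.0980; √(1158 × 0.0884) × 0.2877 − 1.96 = 0.951; power 0.829. Across the three shares, power is 0.832, 0.831, 0.829 at HR 0.75 and 0.622, 0.620, 0.619 at HR 0.80. The pregnant group limits the information, so little is lost.

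**The case against.** The strongest reply is that the effect on the primary endpoint is small. DFS hazard ratios of 0.96–0.99 at 2–5% stage IV are minor beside the planned 0.75–0.80, and DFS type I error mostly stays near nominal. This stands for DFS in most scenarios. At the extreme it is less comfortable: ln(0.93)/ln(0.80) = 0.0726/0.2231, about a third of the smaller planned effect.

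Several stronger readings are tempting, and the documents do not support them:

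- A reader might infer that DFS cannot be computed for these women. Distant metastases and death are both listed events, so a day-0 event is computable. What is missing is a stated rule.
- A reader might infer that an excess of early events in non-pregnant women drives the bias. That would apply to a fixed two-group comparison. With pregnancy time-varying, the earliest events carry almost no weight; the bias comes from stage IV women still at risk once pregnancies accrue.
- A reader might infer that both analyses are equally exposed. The disease-free-interval condition largely screens these women out of the matched analysis, provided the interval is read as zero.
- A reader might infer that the pregnancy rate is distorted. That objective concerns BRCA-mutated patients without a stage limit, and the breadth is intended. Dropping stage IV there changes the target population and does not correct an error.

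The wording also leans towards early disease, with references to survivors and to (neo)adjuvant therapy. These are hints, not eligibility rules, and deliberate breadth in enrolment does not define an endpoint.

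**Conclusion.** The point holds for the pregnancy-impact survival analyses. As written, women metastatic at diagnosis enter the extended Cox comparison of DFS, BCSS and OS, and DFS has no rule for them. Where bias arises, it favours pregnancy. For DFS it is small: an HR of about 0.93–0.99 when the truth is 1.0, and none under day-0 scoring. For OS it is larger: an HR of about 0.8–0.99, with type I error up to about 20%. The missing rule is plain from the text. The sizes rest on assumed stage IV shares of 2–8%, assumed prognosis, and no conception among these women. It should be settled before analysis, more for the definition of the primary endpoint and for the mortality endpoints than for the DFS estimate itself.

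**What to change.** In Section 4 and the Synopsis, state that the DFS, BCSS and OS analyses of pregnancy impact, both extended Cox and matched, include only women without distant metastases at diagnosis, identified from the disease stage already collected. Keep stage IV women in the study for the descriptive objectives; Section 3.1 need not change. Whether they stay in the pregnancy-rate estimate is a choice of target population, to be stated either way.

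The cost is one sentence, no new data and a few percent fewer women in the survival models. Power at HR 0.75 stays at about 0.83.
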